9.7. Rescue Therapy

Additional HBV therapy may be initiated at the discretion of the investigator in the following circumstances:

- Hepatitis B flare defined as abrupt rise in ALT greater than 10x upper limit of normal.
- Evidence of liver decompensation with bilirubin greater than 2x upper limit of normal, prolongation of PT greater than 1 second associated with hepatitis B reactivation, confirmed by repeated test within 4 weeks apart.
- Evidence of clinical liver decompensation with development of ascites, encephalopathy, variceal bleeding.

9.8. Virology Testing and Plan for Monitoring Resistance

A central laboratory will perform all clinical virology testing. All virologic assessments will be performed using an FDA-approved or FDA-cleared assays. Quantitative HBsAg will be determined via a chemiluminescent immunoassay. In the case of virologic failure on treatment (quantifiable HBV DNA after being less than LLOQ), genotypes and phenotypes of Baseline and virologic failure isolates will be determined, and newly emerged drug resistance-associated substitutions/mutations will be identified.

10. DATA MANAGEMENT

10.1. Electronic Data Entry

Data will be transcribed from source documents into an electronic data capture (EDC) system.

The responsible study monitor(s) will verify data, which can be performed remotely or at the clinical study site. The Investigator will ensure that the data recorded are accurate and complete.

Queries emerging during data cleaning will be generated within the EDC system by data management or clinical research associates. The Investigator or his/her designee will answer the queries and update the source data, if needed.

Adverse events and comorbid conditions will be coded by data management using the latest version of the Medical Dictionary for Regulatory Activities (MedDRA); medications will be coded by data management using the World Health Organization (WHO) DRUG dictionary.

After the Last Subject Last Visit (LSLV) has taken place, the database will be cleaned as necessary. As soon as the database is considered clean, it will be locked. The locked database will be used in the final statistical analysis for study reporting. Measures will be undertaken to protect subject data handled during inspections against disclosure to unauthorized third parties. Subject confidentiality will be maintained at all times.

10.2. Protocol Deviations

Protocol deviations will be documented by the Investigator, reported to the institutional review board (IRB) as appropriate, and also reviewed by the assigned clinical research associate (CRA). Deviations will be reported in the clinical trial management system. Each deviation will be classified as major or minor according to the following definitions:

Major protocol deviation: A deviation that has an impact on subject safety, may substantially alter risks to subjects, may have an effect on the integrity of the study data, or may affect the subject's willingness to participate in the study.

Minor protocol deviation: All other protocol deviations.

10.3. Data Quality Assurance

The accuracy and reliability of the study data will be assured by the selection of qualified Investigators and appropriate study centers, review of protocol procedures with the Investigator and associated personnel prior to the study, and by periodic monitoring visits by the Sponsor. Written instructions will be provided for collection, preparation, and shipment of samples.

The monitor will review the source data for accuracy and completeness, and any discrepancies will be resolved with the Investigator or designee, as appropriate.

The Sponsor will be entitled to inspect and audit the facilities used in the clinical and laboratory parts of the study, as well as to make anonymized copies of all the data files pertaining to the study. Similar procedures may also be conducted by agents of any regulatory body, either as part of a national Good Clinical Practice (GCP) compliance program or to review the results of this study in support of a regulatory submission. The Investigator should immediately notify the Sponsor if they have been contacted by a regulatory agency concerning an upcoming inspection.

11. STATISTICAL CONSIDERATIONS

11.1. Sample Size Calculation

The study is designed to evaluate the safety and efficacy of three different NTZ treatment regimens compared to placebo as add-on therapy to TDF, TAF or ETV in reducing quantitative HBsAg (in order to select a dose for future clinical trials).

A student's t-test with a 0.05 two-sided significance level will have 90% power to detect the difference between a mean change of 0.5 log10 for one treatment group and no change for the other treatment group when sigma (common standard deviation) is 0.33 and the sample size in each group is 10. A sample size of 12 per group was selected in order to allow for the possibility of up to 2 non-evaluable subjects per group (due to drop-out, etc.).

11.2. Efficacy Variables

Primary Efficacy Parameter: The mean change in qHBsAg from Baseline to Week 12.

Secondary Efficacy Parameters:

- i. Sustained HBsAg loss with suppression of HBV DNA for 24 weeks after the end of treatment.
- ii. Change in qHBsAg from Baseline to different time points on treatment.
- iii. HBsAg loss.
- iv. HBsAg seroconversion.
- v. HBV DNA suppression.
- vi. Change from Baseline in Fibrosis 4 (FIB-4) score.
- vii. Change from Baseline in FibroScan® score.

11.3. Response Definitions

HBsAg Loss: HBsAg below the lower limit of detection.

HBsAg seroconversion: Loss of HBsAg and gain of anti-HBs.

HBV DNA suppression: HBV DNA less than lower limit of quantitation; target not detected.

11.4. Statistical Methodology

The statistical methodology is described briefly below and will be described in detail in the Statistical Analysis Plan.

11.4.1. Efficacy Analyses

The study will be unblinded to the Sponsor (Romark) and Medical Monitor for analysis of efficacy and safety data after all subjects have completed 12 weeks of treatment and complete data is collected through that time point. The investigators, subjects and monitors will remain blinded throughout the study.

Efficacy analyses will be based on a population consisting of all subjects randomly assigned to the study (“intent-to-treat” population). In the event that there are significant numbers of subjects who fail to complete the study, violate the protocol, or are noncompliant with the study medication, efficacy analyses will also be conducted for a population excluding these subjects (“per protocol population”).

Primary efficacy analyses will be conducted as follows: For each NTZ treatment group, the mean change in qHBsAg from Baseline to Week 12 will be compared to that of the placebo treatment group.

Secondary efficacy analyses will be conducted as follows:

- For each of the three NTZ groups, the proportion of subjects with sustained suppression of HBV DNA and HBsAg loss at 24 weeks after the end of treatment will be compared to the proportion for the placebo treatments group.
- For each NTZ dose group and for each study time point, the change in qHBsAg from Baseline will be compared to the change in qHBsAg for the placebo treatment group.
- For each of the three NTZ groups and for each study time point, the proportion of subjects with HBsAg loss will be compared to the proportion for the placebo treatments group.
- For each of the three NTZ groups and for each study time point, the proportion of subjects with HBsAg seroconversion will be compared to the proportion for the placebo treatments group.
- For each of the three NTZ groups and for each study time point, the proportion of subjects with quantifiable HBV DNA at Baseline who experienced HBV DNA suppression will be compared to the proportion for the placebo treatments group.
- For each NTZ dose group and for each study time point, the mean change in Fibrosis 4 (FIB-4) score from Baseline will be compared to the change for the placebo treatment group.
- For each NTZ dose group, the mean change in FibroScan® score from Baseline to end of treatment and to end of off-treatment follow-up will be compared to the change for the placebo treatment group.

Means will be compared by two-sided student’s t tests, $\alpha = 0.05$. Nonparametric data will be analyzed using the Wilcoxon rank sum (Mann-Whitney) test. Proportions will be compared using a two-sided Fisher’s Exact test, $\alpha = 0.05$. In the setting of an early Phase 2 study, no adjustments for multiplicity are planned.

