7.1. Inclusion Criteria

1. Age at least 21 years.
2. CHB virus infection (serum HBsAg-positive for at least 6 months or serum HBsAg positive and negative immunoglobulin M (IgM) antibodies to HBV core antigen (IgM anti-HBc).
3. HBeAg negative.
4. Virologically suppressed (HBV DNA less than the lower limit of quantitation) for at least 12 months on TDF, TAF or ETV therapy.
5. Quantitative HBsAg greater than 100 IU/mL.
6. ALT below 1.5 times the upper limit of normal.
7. Able to comply with the study requirements.

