9.1. Pre-study Evaluation (Day -31 to 1)

Before screening, subjects will be informed of the nature of the study, and written consent must be obtained prior to participation. After obtaining informed consent, the following procedures will be carried out:

1. Complete medical history
2. Physical examination, including height, body weight and vital statistics
3. Urine pregnancy test for all females of child-bearing potential
4. Review concomitant medications
5. Collection of blood sample for serological tests for qHBV DNA, qHBsAg, qAnti-HBs, HBeAg, anti-HBe, IgM anti-HBc, anti-HIV, anti-HCV and anti-HDV.
6. Collection of a blood sample for laboratory tests including hemoglobin, hematocrit, complete blood count (total and differential), platelet count, prothrombin time (PT), international normalized ratio (INR), random/faasted blood sugar, total cholesterol, high-density lipoprotein, triglycerides, albumin, iron, ferritin, aspartate aminotransferase (AST), ALT, gamma glutamyl transferase (GGT), creatine phosphokinase (CPK), alkaline phosphatase, bilirubin (total/direct), blood urea nitrogen (BUN), creatinine, sodium, potassium, chloride, and alpha-fetoprotein (AFP).
7. Collection of urine sample for routine urinalysis (appearance, glucose, protein and blood).
8. Calculation of creatinine clearance by the Cockcroft-Gault equation using ideal body weight.
9. FibroScan® test.
10. Ultrasonography for hepatocellular carcinoma (HCC) screening.
11. Confirmation that the subject satisfies all inclusion/exclusion criteria.

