9.2. Baseline (Day 1)

At Baseline, the following procedures will be carried out:

1. Physical examination, including body weight and vital statistics.
2. Urine pregnancy test for all females of child-bearing potential.
3. Review concomitant medications.
4. Collection of a blood sample for qHBV DNA, qHBsAg, qAnti-HBs, HBeAg, anti-HBe and anti-HIV (anti-HIV is only for subjects at high risk of contracting HIV according to the discretion of the investigator).
5. Collection of a blood sample to be stored for exploratory analyses of HBV RNA, HBV core-related antigen (HBcrAg), qAnti-HBc, quantitative cccDNA, HBs fragments, HBsAg-anti-HBs immune complex, immunological studies and/or host DNA (to assess relationships with virologic response).
6. Collection of a blood sample for laboratory tests including hemoglobin, hematocrit, complete blood count (total and differential), platelet count, PT, INR, albumin, AST, ALT, GGT, CPK, alkaline phosphatase, bilirubin (total/direct), BUN, creatinine, sodium, potassium, chloride, and AFP.

7. Collection of blood samples for trough (just prior to dosing) plasma levels of NrtI and tizoxanide.
8. Collection of a urine sample for routine urinalysis (appearance, glucose, protein and blood).
9. Obtain a 12-lead electrocardiogram (ECG).
10. Instruct the subject regarding:
 - a. Administration of study medication.
 - b. Use of birth control. Female subjects of childbearing potential, if sexually active, will be instructed to continue an acceptable method of birth control for the duration of the study and for one month post-treatment. Acceptable methods of birth control include a double barrier method, oral birth control pills, an IUD, or medroxyprogesterone acetate administered intramuscularly.
 - c. Study visits. Subjects will be provided instructions for returning to the clinic for study visits.
 - d. Seeking emergency care or contacting the study physician or nurse. Subjects must be instructed to seek emergency medical care or contact the study physician or nurse if he/she develops any of the following symptoms during the study (treatment period or off-treatment follow-up period).
 - CALL 911 (United States) or LOCAL EMERGENCY SERVICES (outside the United States) OR HOSPITAL OR CONTACT STUDY PHYSICIAN IF YOU HAVE:
 - Trouble breathing including shortness of breath.
 - Severe pain in your chest, shoulder or belly.
 - CALL STUDY NURSE OR PHYSICIAN IF YOU EXPERIENCE:
 - Fever that does not go away or gets higher.

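### The only stand-alone analysis of HBV DNA suppression counts subjects with quantifiable HBV DNA at Baseline, whom the inclusion criteria keep out of the trial

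*Combined protocol and SAP*

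**What the plan says.** Section 11.2 lists HBV DNA suppression as secondary parameter v, with no restriction to a subset. Section 11.4.1 adds one: for each NTZ group and each time point, "the proportion of subjects with quantifiable HBV DNA at Baseline who experienced HBV DNA suppression will be compared" with placebo. Section 11.4.1 also sets the general population: "Efficacy analyses will be based on a population consisting of all subjects randomly assigned to the study". Proportions are compared by a two-sided Fisher's exact test at 0.05.

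Inclusion criterion 4 (Section 7.1) requires subjects to be "Virologically suppressed (HBV DNA less than the lower limit of quantitation) for at least 12 months on TDF, TAF or ETV therapy". HBV DNA is measured in the screening window, headed "Pre-study Evaluation (Day -31 to 1", and again on Day 1, where Section 9.2 lists "Collection of a blood sample for qHBV DNA, qHBsAg, qAnti-HBs, HBeAg, anti-HBe and anti-HIV". Section 9.3 repeats the test at every treatment visit.

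Section 11.3 defines the response as "HBV DNA suppression: HBV DNA less than lower limit of quantitation; target not detected". HBV DNA suppression appears in one other efficacy comparison, the composite "the proportion of subjects with sustained suppression of HBV DNA and HBsAg loss at 24 weeks after the end of treatment". Loss of suppression appears in Section 9.8 only as a trigger for resistance testing: "In the case of virologic failure on treatment (quantifiable HBV DNA after being less than LLOQ), genotypes and phenotypes of Baseline" and failure isolates are to be determined.

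**The concern.** The bullet asks how many viraemic subjects become suppressed, in a trial that enrols subjects who are already suppressed. The question that fits this population is whether suppression is kept while NTZ is added to the nucleos(t)ide therapy. The bullet cannot answer that on either reading:

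- **Over the subset quantifiable at Baseline**, the denominator is close to zero.
- **Over all randomised subjects**, a subject suppressed at Baseline can never enter the numerator, so keeping and losing suppression score the same.

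A listed secondary parameter would therefore have no informative result. The data to describe maintained suppression are collected throughout, yet no stated by-arm analysis uses them.

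**Working it through.** **Inputs from the documents.** 12 subjects per arm (Synopsis); two-sided Fisher's exact test, alpha 0.05 (Section 11.4.1); HBV DNA below LLOQ at entry (Section 7.1). Section 11.1 gives 90% power for the primary t-test with 10 per group, difference 0.5 log10 and SD 0.33. A noncentral-t calculation gives 89.3%, which agrees. The documents give no figure for HBV DNA suppression.

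**Can the subset contain anyone?** Screening can precede Day 1 by up to 31 days and HBV DNA is tested at both, so a quantifiable Day 1 value is possible without an eligibility violation. Otherwise only violations fill the subset. If everyone meets criterion 4 on Day 1, the count is 0 of 48.

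**Assumption.** Let r be the share quantifiable on Day 1. The documents do not give it, so a range is shown. Counts per arm are taken as independent Bin(12, r).

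**Subset reading.** Take the most favourable outcome: all a subjects suppressed in one arm and none of b in the other. Fisher p-values are:

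| a v b | p |
|---|---|
| 3 v 3 | 0.10 |
| 2 v 4 | 0.067 |
| 1 v 12 | 0.077 |
| 2 v 5 | 0.048 |
| 3 v 4 | 0.029 |

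So p<0.05 needs at least 7 quantifiable subjects across the two arms, with at least 2 in each. The chance that the counts permit this is the sum of P(a)P(b) over all pairs (a, b) with p<0.05.

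**All-randomised reading.** 4/12 v 0/12 gives p = 0.093; 5/12 v 0/12 gives p = 0.037. At least 5 of 12 in one arm must therefore be quantifiable at Baseline. The chance is 1 − (1 − P(Bin(12, r) ≥ 5))². At r = 10%, P(Bin ≥ 5) = 0.00433, so the chance is 1 − (0.99567)² = 0.0086.

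| Assumed r | Expected per arm (12r) | Subset reading | All-randomised reading |
|---|---|---|---|
| 2% | 0.24 | <0.001% | <0.001% |
| 5% | 0.6 | 0.01% | 0.04% |
| 10% | 1.2 | 0.7% | 0.9% |
| 20% | 2.4 | 18% | 14% |

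These are chances per pair of arms that significance is possible at all; they are not power. Section 8 allows replacements. If these took both arms to 14, the chances at r = 10% would be 1.7% (subset) and 1.8% (all randomised).

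**Does the definition in Section 11.3 rescue the bullet?** Subjects below LLOQ with target detected meet criterion 4, are not suppressed under Section 11.3, and could become so. But they are not quantifiable, so the bullet leaves them out.

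**What the replacement can show.** 12/12 has an exact 95% lower limit of 0.025^(1/12) = 0.735, giving 73.5% to 100%. Against 12/12 on NTZ, 8/12 on placebo gives p = 0.093 and 7/12 gives p = 0.037. If true suppression is 100% on NTZ, power is P(placebo count ≤ 7): 0.4%, 7% or 28% for true placebo suppression of 90%, 80% or 70%.

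**The case against.** - **The stakes are small.** This is one of seven secondary parameters in a Phase 2 trial with 12 per arm and no multiplicity adjustment, and Section 9.8 already picks out virologic failures for resistance testing. This is true and limits the severity. But Section 9.8 plans no by-arm summary, and the replacement's low power does not excuse an analysis that cannot show lost suppression at all.
- **The bullet may have meant detectable rather than quantifiable.** It would then be a coherent analysis of gaining target-not-detected status. The documents do not show that intent, and the stated word excludes those subjects. The fix keeps this analysis as a separate row.
- **Under the Section 11.3 definition, a proportion in all randomised subjects mixes Baseline status with change.** This stands: a subject target-detected at Baseline counts as unsuppressed without having lost anything. The below-LLOQ and virologic-failure rows are therefore needed to show maintenance. The 12/12 illustration assumes that every NTZ subject meets whichever definition is used; eligibility supports that starting point only for below LLOQ.
- **Three comparisons are planned, not one.** At r = 10% and 12 per arm, the chance that at least one permits p<0.05 is 1.9% (subset) or 1.7% (all randomised); at 20% it is 36% or 26%. The conclusion is unchanged at low rates.
- **Section 11.4 defers detail to a Statistical Analysis Plan.** Any such detail beyond the supplied text cannot be judged here. The bullet, however, is a stated rule, and following it carries the defect forward.

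**Conclusion.** The concern holds and should be fixed. As written, the only stand-alone analysis of HBV DNA suppression has by design about 0 of 12 contributors per arm. That rests on criterion 4 being met on Day 1. Allowing assumed Day 1 quantifiable rates up to 10%, the chance that a pair of arms could reach p<0.05 stays below 1% with 12 per arm on either reading. It becomes appreciable (14% to 18%) only at an assumed 20%. The defect is confined to one secondary parameter: the primary endpoint, the sample size and the quantitative HBsAg comparisons are untouched.

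**What to change.** In the Section 11.4.1 bullet, delete the phrase restricting the analysis to subjects quantifiable at Baseline. Then, by arm and visit in all randomised subjects:

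1. Report the number and proportion with HBV DNA suppression as defined in Section 11.3, with exact 95% confidence intervals and the number missing.
2. Tabulate subjects below LLOQ, and virologic failures as described in Section 9.8.
3. If Section 11.3 keeps the target-not-detected condition, also report the proportion reaching it among subjects below LLOQ but target-detected at Baseline.
4. State beside results after Week 12 that discontinuation based on quantitative HBsAg (Section 9.6, item 4) affects them.

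Sections 7.1 and 11.3 describe suppression differently, and the term also appears in Sections 6, 9.4, 9.6 and Appendix II. The sponsor should reconcile these passages; no clinical rule is proposed here.

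The cost is one reworded bullet and added table rows, with no new samples or visits. The result is mainly descriptive, given the interval and power shown above, and the target-detected row may be small because the documents do not say how many such subjects to expect.

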6. STUDY DESIGN

The study will be a randomized, double-blind, placebo-controlled design. Forty-eight subjects will be selected according to the inclusion and exclusion criteria listed below. Upon enrollment in the study, subjects will be randomized to one of the following treatment groups (12 subjects per group):

- Group 1: PLACEBO

Subjects will take three placebo tablets twice daily.

- Group 2: 600 mg NTZ once daily (QD).

Subjects will take two NTZ 300 mg extended release tablets and one placebo tablet in the morning and three placebo tablets in the evening.

- Group 3: 600 mg NTZ twice daily (BID).

Subjects will take two NTZ 300 mg extended release tablets and one placebo tablet twice daily.

- Group 4: 900 mg NTZ BID.

Subjects will take three NTZ 300 mg extended release tablets twice daily.

NTZ and placebo tablets will be administered orally with food. All subjects will continue TDF, TAF or ETV therapy throughout the study.

After 12 weeks, subjects will continue treatment with the same treatment regimen if they have achieved any decline in quantitative HBsAg (qHBsAg) from Baseline to Week 12. The subjects will discontinue treatment with the investigational medication (NTZ and/or placebo) due to:

- Adverse events
- Withdrawn consent
- Noncompliance
- The subject fails to achieve any decline in qHBsAg from Baseline to Week 12, at least a 0.5 log₁₀ decline from Baseline to Week 24, at least a 1 log₁₀ decline from Baseline to Week 48, at least a 2 log₁₀ decline from Baseline to Week 72 or HBsAg loss at Week 96.
- The subject experiences HBsAg loss with HBV DNA suppression maintained on treatment for 24 weeks (consolidating therapy). TDF, TAF or ETV therapy will also be discontinued.

Subjects will return to the clinic at Day 3, Weeks 1, 2, 4, 8, 12, 16, 20, 24 and every 12 weeks thereafter during the treatment period. Blood samples will be collected at each visit for laboratory and/or serology tests. Blood samples for trough (just prior to dosing) plasma levels of NrtI and tizoxanide will be collected at Baseline and each scheduled visit while on therapy.

Subjects will return to the clinic for off-treatment follow-up at 4, 8 and 12 weeks following the end of treatment with investigational medication (NTZ and/or placebo). In the event that a subject has sustained HBsAg loss with HBV DNA suppression at the Week 12 follow-up visit, that subject will return for additional follow-up visits 24 and 48 weeks after the end of treatment.

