9.4. Follow-up After End of Treatment with NTZ/Placebo

Subjects will return to the clinic for follow-up evaluation 4, 8 and 12 weeks after the end of treatment with the investigational medication (NTZ/placebo). In the event that a subject has sustained HBsAg loss with HBV DNA suppression at the Week 12 follow-up visit, that subject will also return for additional follow-up visits at 24 and 48 weeks after the end of treatment. The following evaluations will be performed during each follow-up visit:

1. Brief physical examination including body weight and vital statistics.
2. Review concomitant medications.
3. Collection of blood sample for qHBV DNA, qHBsAg, qAnti-HBs, HBeAg, anti-HBe and anti-HIV (anti-HIV is only for subjects at high risk of contracting HIV according to the discretion of the investigator).
4. Collection of blood sample to be stored for exploratory analyses of HBV RNA, HBcrAg, qAnti-HBc, quantitative cccDNA, HBs fragments, HBsAg-anti-HBs immune complex, immunological studies and/or host DNA (to assess relationships with virologic response).
5. Collection of blood sample for laboratory safety: hemoglobin, hematocrit, complete blood count, (total and differential), platelet count, PT, INR, AST, ALT, GGT, CPK, alkaline phosphatase, bilirubin total/direct, albumin, BUN, creatinine, sodium, potassium, chloride, and AFP.
6. Collection of urine sample for routine urinalysis (appearance, glucose, protein and blood).
7. FibroScan® testing (at end of follow-up only).
8. Ultrasonography for HCC screening (every 6 months).
9. Review of adverse events/side effects.

All adverse events must be followed up until they resolve or have stabilized (even beyond the follow-up visit dates provided above).

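### FIB-4, HBsAg loss and seroconversion are tested against placebo at every time point, but response-based stopping and 12-week follow-up leave about half the placebo arm at Week 36 and at most about one subject from Week 48

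*Combined protocol and SAP*

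**What the plan says.** **Stopping.** Sections 6 and 9.6 end study drug in any arm, placebo included, at fixed landmarks. The first in Section 6 is "The subject fails to achieve any decline in qHBsAg from Baseline to Week 12". Later ones require a decline of 0.5 log10 at Week 24, 1 log10 at Week 48 and 2 log10 at Week 72, and HBsAg loss by Week 96.

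**Follow-up.** Section 9.4: "Subjects will return to the clinic for follow-up evaluation 4, 8 and 12 weeks after the end of treatment with the investigational medication". Visits 24 and 48 weeks after treatment are only for subjects with sustained HBsAg loss and HBV DNA suppression. Table 4 numbers off-treatment visits from the end of treatment, separately from treatment weeks.

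**Analysis.** Section 11.4.1 bases efficacy on all randomised subjects. For FIB-4: "For each NTZ dose group and for each study time point, the mean change in Fibrosis 4 (FIB-4) score from Baseline will be compared" with placebo. For HBsAg loss: "for each study time point, the proportion of subjects with HBsAg loss will be compared to the proportion for the placebo treatments group". Seroconversion has the same wording. Means are compared by t-test and proportions by Fisher's exact test. The section does not define a study time point, set a last one, or say how a subject with no further visits is handled. Section 11.4 leaves detail to a Statistical Analysis Plan; the document reviewed contains no such rule.

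**The concern.** Whether a subject has a visit at Week 36 or later depends on his or her earlier qHBsAg change. If NTZ lowers qHBsAg as planned, that makes observation depend on arm. A late comparison would then set most of an NTZ arm against the few placebo subjects whose qHBsAg happened to fall. It would no longer be a comparison of randomised groups, and a trend over visits could reflect only who is still being seen.

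Counting off-drug values does not repair this. After the last follow-up visit there is no value of any kind. The all-randomised population does not help FIB-4 either, because a randomised subject without a visit contributes no score.

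**Working it through.** **1. The plan's own figure.** Section 11.1 assumes "a mean change of 0.5 log10 for one treatment group and no change for the other treatment group", where "sigma (common standard deviation) is 0.33 and the sample size in each group is 10", and says that the test "with a 0.05 two-sided significance level will have 90% power". The noncentrality is 0.5 / (0.33 × √(2/10)) = 3.39 on 18 df, which gives 89.3% power. The stated 90% is reproduced, so these inputs are used below, with 12 randomised per arm.

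**2. Last scheduled visit from Baseline.** Stop at Week 12: Week 12 + 12 = Week 24. Stop at Week 24: Week 36. On-treatment visits after Week 24 fall at Weeks 36, 48, 60 and so on. A visit at Week 36 therefore needs the Week 12 rule to be passed, and a visit at Week 48 needs the Week 24 rule to be passed as well. This leaves aside sustained HBsAg loss, which Section 4.1 puts below 1% on the background drugs.

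**3. Assumptions not in the documents.** Normal changes, the same SD of 0.33 at later landmarks, correlation between landmark changes of 0 to 0.9, and no other drop-out.

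**4. Placebo (mean change 0).**
- Week 36: P(any decline at Week 12) = 0.50; 12 × 0.50 = 6 subjects (binomial 95% range 3 to 9).
- P(decline of at least 0.5 at Week 24) = P(Z > 0.5/0.33 = 1.515) = 0.065.
- Week 48, both rules passed: 0.50 × 0.065 = 0.032 at correlation 0, rising to 0.065 at 0.9; 12 × these = 0.4 to 0.8 subjects.
- P(no placebo subject at Week 48) = (1 − 0.065)^12 to (1 − 0.0324)^12 = 45% to 67%. P(at most one) = 82% to 94%.

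**5. NTZ arm with the planned 0.5 log10 decline at Week 12.**
- Week 36: P(Z < 1.515) = 0.935; 12 × 0.935 = 11.2.
- Week 48, mean stays at 0.5: 0.935 × 0.5 = 0.468, up to 0.50 with correlation; 5.6 to 6.0.
- Week 48, mean decline 1 log10 by Week 24: 0.935² = 0.874, up to 0.91; 10.5 to 11.0.

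| Seen, of 12 | To Week 24 | Week 36 | Week 48 |
|---|---|---|---|
| Placebo | 12 | 6 | 0.4 to 0.8 |
| NTZ, planned effect | 12 | 11.2 | 5.6 to 11.0 |
| NTZ, no effect | 12 | 6 | 0.4 to 0.8 |

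The 12 at Week 24 needs off-treatment visits 4, 8 and 12 of Week 12 stoppers to be read as Weeks 16, 20 and 24.

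**6. Sensitivity.** With a placebo decline of 0.05 log10 at Week 12 and SD 0.1, about 8.3 placebo subjects are seen at Week 36 and none at Week 48. With declines of 0.05 then 0.1 log10 and SD 0.33, the figures are 6.7, then up to 1.3.

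**7. What Fisher's test can show.** On observed cases with one placebo subject, the smallest possible p is 1/13 = 0.077 (12 vs 1) or 1/7 = 0.143 (6 vs 1). Over all randomised subjects, 5/12 vs 0/12 gives p = 0.037.

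**The case against.** - **Half the placebo arm is still there between Weeks 24 and 36.** This stands. A reader might infer that placebo is barely observed after Week 24. The schedule does not support that: Week 24 stoppers are followed to Week 36. Week 24 is only the last point with complete coverage.
- **HBsAg loss and seroconversion can survive the missing visits.** This stands. A reader might infer that these tests must also end at Week 24. But the population is all randomised subjects, those stopped for poor response are HBsAg-positive at the stop (Section 9.6), and background loss is below 1% (Section 4.1). Counting them as non-responders is a workable convention. The plan does not state it.
- **The coverage figures depend on a visit mapping.** This stands. With Table 4's labels, about half the placebo arm has already left the treatment schedule at Week 16. That moves the start of the problem earlier; it does not remove it.
- **Bias in FIB-4 is not demonstrated.** Partly stands. Retention differs by arm only if NTZ lowers qHBsAg, and bias also needs FIB-4 change to be related to qHBsAg change, on which the documents are silent. The loss of the placebo group needs neither condition.
- **Early Phase 2, unadjusted secondary tests, primary endpoint untouched.** True, and it limits the weight of the point. A test with no placebo subjects fails visibly, but the Week 36 FIB-4 test would run and look ordinary.

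**Conclusion.** The concern holds in a limited form. As written, Section 11.4.1 calls for FIB-4 comparisons that are response-selected at Week 36 (about 6 placebo subjects against about 11 on an effective NTZ arm) and that from Week 48 usually have no more than one placebo subject. For HBsAg loss and seroconversion the fault is a missing counting rule, not a comparison that cannot be made.

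The sizes rest on the plan's mean and SD, the same SD at later visits, correlation of 0 to 0.9 and no other drop-out. Other inputs tried leave at most 1.3 placebo subjects at Week 48, so the conclusion there is stable. It would be too strong to say that the late contrasts favour NTZ: with no NTZ effect the arms empty alike, and the direction of any FIB-4 bias is unknown. The primary comparison is unaffected, because the first response-based stop comes at Week 12 itself. The plan should be changed on this point, but it does not threaten the trial's main result.

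**What to change.** Change Section 11.4.1, and carry the same rules into the detailed analysis plan:

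1. Define study time points as weeks from Baseline, and match off-treatment visits 4, 8 and 12 of Week 12 stoppers to Weeks 16, 20 and 24.
2. Limit formal placebo-controlled FIB-4 tests to time points up to Week 24. Report later visits by arm descriptively, with the number observed.
3. For HBsAg loss and seroconversion, compare the cumulative number achieving the event among all randomised subjects. Count those no longer observed as non-responders, and keep Fisher's exact test on that count at later time points.

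The cost is wording only, with no extra visits or subjects and no change to the stopping rules. The downside is that there is no formal FIB-4 test after Week 24, where the placebo group is about half or less and selected on response. The non-responder rule would also miss any loss that occurs after a subject's last visit.
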